9 STUDY CALENDAR

PERIOD	Pre-Study ^a	Phase 0 Microdose		Cycle 1 + Microdose			Ongoing Treatment		Off Study
		Day 1	Day 2	Day 1	Day 2	Day 3	Cycle 2, Day 1	Ongoing Treatment	
Safety Assessments.^b See Section 7.1									
History & Physical Exam	X			X			X	*	
Vital Signs	X	X		X			X	*	
Performance Status	X			X			X		
Hematology	X	X		X			X	*	
Serum Chemistries	X	X		X			X	*	
Pregnancy Test	X								
Adverse Events. See Section 7.2									
Adverse Events		X-----X							
Efficacy Assessments. See Section 7.3									
Imaging Studies	X						X ^c	X	
Treatments. See Section 6.									
[¹⁴ C]Oxaliplatin Microdose		X		X					
FOLFOX				X-----X			X	*	
Biologic Agent, if appropriate						X		*	
Correlative Studies. See Sections 6.3.3, 6.4.2 and 10.1									
Plasma Pharmacokinetics		X	X	X	X	X			
PBMCs		X	X	X	X	X			

^a Pre-study assessments within 14 days before registration, except for imaging studies within 28 days of registration

^b All on study safety assessments may be performed +/- 72 hours of the indicated timepoint

^c Every 8 weeks (+/- 1 week) for 6 months then every 12 weeks (+/- 2 weeks) until progression. Required only in patients with measurable disease at baseline.

* After Cycle 2, Day 1 and resolution of all microdose-associated toxicities, all safety assessments and treatments are at the discretion of the treating investigator according to good medical practice.

[figure not shown]
10 SPECIAL INSTRUCTIONS

10.1 Specimen Collection, Storage, Shipping and Submission Requirements

10.1.1 Collection Method and Storage

One 8-ml blood specimen will be collected into a BD Vacutainer CPTTM tube with sodium heparin (Becton Dickinson products # 362753) through an indwelling temporary venous catheter at the time points described in **Table 2** and **Table 3**. The tube will be gently inverted several times to ensure mixing with heparin anticoagulant. The tube will be immediately put on ice. To isolate plasma, the tubes are centrifuged at room temperature in a horizon rotor for 25 minutes at 1600 X g. After centrifugation, plasma is located at the top of the specimen (**Figure 3**), and will be transferred to two polypropylene cryogenic vials. The vials will be labeled with patient's identification information and stored at or below -70°C until shipping. After collection of all of the specimens from the same patients, the ¹⁴C content in plasma is determined by liquid scintillation count. The oxaliplatin concentration is calculated based on the ¹⁴C content in the plasma specimens.

Figure 3. Centrifugation to separate Plasma and Mononuclear Cells in Peripheral Blood

After most of the plasma is removed for PK study, PBMC will be transferred to another tube, washed twice with ice-cold phosphate-buffered solution (PBS) with 2% fetal calf serum. DNA will be extracted from PBMC as described before [67], and sent to Accelerated Medical Diagnostics and LLNL for Pt-DNA adduct measurement.

10.1.2 Shipping and Submission Requirements

The peripheral blood specimens can be immediately kept at 4°C or on ice up to four hours before the plasma and PBMC are separated. Plasma will then be stored at -70°C freezer until PK studies. PBMC will be used for DNA extraction immediately after separation.

10.2 Pharmacokinetics

10.2.1 Specimens & Collection Frequency

Blood specimens will be collected at the time points outlined in **Table 2** and **Table 3**.

Plasma will be used for PK assessment. Since a very small fraction of oxaliplatin is metabolized at the terminal phase, we will not determine the terminal half-lives if they are longer than 24 hours.

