In phase I studies, the calculated exposure or area under the curve (AUC) of oxaliplatin administered at 85 mg/m² averaged 4.68 µg/mL/hr; however, there was significant inter-patient variation in AUC (SD 1.40 µg/mL/hr). The metabolism of oxaliplatin occurs in a triphasic manner. The initial ($T_{1/2\alpha}$), second ($T_{1/2\beta}$) and terminal ($T_{1/2\gamma}$) phase half-lives of oxaliplatin are reported to be 25.8 minutes, 16.8 hours and 391 hours, respectively [8, 9]. Approximately half of oxaliplatin is excreted in urine within the first 6 hours. Only a small fraction of oxaliplatin is excreted at the terminal phase. Because the formation of Pt-DNA adducts correlated to the concentration and incubation time of cells with Pt [10], and because there is a linear correlation between gross levels of platinum bound to DNA and the extent of cytotoxicity [11], it is conceivable that those patients with longer serum half-life of Pt may have more cytotoxic effects. We hypothesize that increased metabolism (short half-life) may be responsible for some cases of resistance to Pt agents. Therefore, a PK study may identify those patients with a short half-life of Pt and help design personalized therapy studies altering the dose of oxaliplatin to overcome resistance.

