8.2 Endpoint Definitions

8.2.1 Primary Endpoint

The primary endpoint is the feasibility of assessing therapeutic pharmacokinetic (PK) parameters of the therapeutic dose using the microdose in evaluable patients. For the purposes of this pilot study, this assessment will be considered feasible if the area under the curve extrapolated to infinity ($AUC_{0\rightarrow\infty}$) of the microdose and the therapeutic dose are within 2-fold of each other when normalized for differences in dose with a 95% confidence interval.

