8.2.2 Secondary Endpoints

Secondary endpoints include:

- 8.2.2.1 Assessment of other PK parameters (e.g. C_{max} , t_{max} , $t_{1/2}$, CL) of the phase 0 microdose compared to the therapeutic dose.
- 8.2.2.2 Comparison of the PK parameters of the phase 0 microdose to the FOLFOX-integrated microdose.
- 8.2.2.3 The association of oxaliplatin-DNA adducts (see **section 10.3**) and tumor response by RECIST 1.1 (see **Appendix C**).
- 8.2.2.4 The association of oxaliplatin-DNA adducts (see **section 10.3**) and duration of disease control (see **Appendix C**).
- 8.2.2.5 Safety according to the Common Terminology Criteria for Adverse Events version 4 (see **section 7.2**).

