11.2 Analysis Plan

11.2.1 Primary Analyses

For the primary endpoint of feasibility is defined in **section 8.2.1**. We will correlate dose normalized $\text{AUC}_{0-\infty}$ parameters from phase 0 microdosing with parameters from the therapeutic dose of oxaliplatin for evaluable patients (the criteria for evaluation are listed in **section 8.1**). While assessment of PK feasibility is the primary endpoint of this study, we will use the totality of the data, including assessment of DNA adduct formation in PBMCs to determine the future development of this assay.

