11.3 Sample Size

The number of subjects required to provide 80% probability that a 95% CI for the ratio of geometric means of full dose and micro dose PK parameters is within 2 fold (i.e., from 0.5 to 2) depends on the coefficient of variation (CV) of the ratio of the parameters, which depends on the CV of each parameter and the within-person correlation between the full dose and micro dose parameters (on a log scale). According to the Lappin et al. [77], CVs for $t_{1/2}$ were in the 0.3-0.5 range for diazepam and midazolam (which had good concordance between doses as well as adequate bioavailability). With these specifications, a sample size of 6 patients receiving both full- and micro-doses is sufficient.

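### Section 10.2.1 declines to determine terminal half-lives over 24 h, yet the primary AUC0-infinity and the secondary CL and t1/2 need a terminal slope, and no other slope or fallback is stated.

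*Combined protocol and SAP*

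**What the plan says.** Section 8.2.1 defines the primary endpoint: "this assessment will be considered feasible if the area under the curve extrapolated to infinity" of the microdose and of the therapeutic dose agree within 2-fold after dose normalisation, with a 95% confidence interval. Section 11.2.1 relates the phase 0 values to "parameters from the therapeutic dose of oxaliplatin for evaluable patients". Section 8.2.2.1 adds Cmax, tmax, t1/2 and CL "of the phase 0 microdose compared to the therapeutic dose".

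Section 10.2.1 then says "we will not determine the terminal half-lives if they are longer than 24 hours". Its reason is given as "Since a very small fraction of oxaliplatin is metabolized at the terminal phase".

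Section 10.2.2 is the only text on the calculation. It lists Cmax, t1/2 and AUC but gives no rule for choosing the slope, no extrapolation method and no fallback such as AUC to the last sample.

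Section 8.1 makes a patient evaluable on receipt of both microdoses and 80% of samples, and replaces patients only for failing that. Sampling ends at 24 h in phase 0 (Table 2) and at 48 h in cycle 1 (Table 3). Sections 2.2, 3.1.4.2 and 3.2.3 quote half-lives of 25.8 min (0.43 h), 16.8 h and 391 h.

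**The concern.** By the usual method, AUC0-infinity is the AUC to the last sample plus the last concentration divided by the terminal rate constant; CL is dose divided by AUC0-infinity; and t1/2 is ln 2 divided by the same constant. A rule not to determine that constant above a threshold removes an input to the primary endpoint and to two secondary ones.

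Complete sampling does not avoid this. A fully sampled patient with a long half-life stays evaluable and is not replaced, but the plan gives no way to compute that patient's primary value. The slope would then be chosen after the data are seen, in a study of 6 patients.

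The t1/2 summaries would also be cut off by their own value, which biases them short. Section 2.2 gives long half-lives some interest: "it is conceivable that those patients with longer serum half-life of Pt may have more cytotoxic effects".

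**Working it through.** **1. The plan's own figure.** Section 11.3 gives N = 6 for 80% probability that the 95% CI of the geometric mean ratio lies within 0.5 to 2. It uses CVs that "were in the 0.3-0.5 range for diazepam and midazolam" and gives no value for the within-person correlation rho. For a true ratio of 1, the SD of the log-ratio is sqrt(ln(1+CV²)) × sqrt(2(1−rho)).
- CV 0.3, rho 0: SD = 0.294 × 1.414 = 0.415; probability at n = 6 is 80.7%.
- CV 0.5, rho 0.7: SD = 0.472 × 0.775 = 0.366; probability at n = 6 is 91.1%.

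N = 6 is thus reproduced under some values of rho. If one primary value were lost and not replaced, the probabilities at n = 5 would be 63.6% and 77.7%.

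**2. Two readings of 'terminal'.**
- *Gamma phase.* Sections 2.2 and 3.1.4.2 use the word for the 391 h phase. At CV 0.3 to 0.5 essentially no patient falls below 24 h, so the half-life is determined for nobody and AUC0-infinity has no defined slope in anyone.
- *Observed slope.* The rule then applies only to patients whose fitted slope is slow.

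**3. What slope would be observed?** I used a tri-exponential model with a 2 h infusion, the protocol's three half-lives and assumed AUC shares (beta 40%, gamma 1%). The fitted half-life depends on the points used:

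| Samples fitted | Fitted t1/2 |
|---|---|
| 3, 4, 24 h | 7.3 h |
| 4, 24 h | 9.9 h |
| 4, 24, 48 h | 12.9 h |
| 24, 48 h | 16.9 h |

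Raising the gamma share to 50% (beta 30%) gives 13.6 h from 4 and 24 h, and 17.1 h from 4, 24 and 48 h. If beta itself is 24 h (assumed shares: beta 20–60%, gamma 1–30%), the fitted value is 7–21 h from 4 and 24 h and 12–23 h from 4, 24 and 48 h. It exceeds 24 h only when the slope is taken from 24 and 48 h alone.

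**4. Chance that the rule bites on the observed-slope reading.** Take t1/2 as lognormal, with CV 0.3 to 0.5 as in 11.3 and an assumed median of 9.7 to 17.1 h. Then P(t1/2 > 24 h) = 1 − Φ(ln(24/median)/sd), with sd 0.294 or 0.472, and P(at least one of 6) = 1 − (1−p)^6.

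| Median | CV | p | At least one of 6 |
|---|---|---|---|
| 9.7 h | 0.3 | 0.1% | 0.6% |
| 9.7 h | 0.5 | 2.8% | 15% |
| 16.8 h | 0.3 | 11.2% | 51% |
| 16.8 h | 0.5 | 22.5% | 78% |
| 17.1 h | 0.5 | 23.6% | 80% |

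**5. Does the stated reason cover these patients?** For a single exponential, the share of post-infusion AUC beyond time t is 0.5^((t−2)/t1/2). At t1/2 = 24 h this is 0.5^(22/24) = 53% beyond 24 h and 0.5^(46/24) = 26% beyond 48 h. At 36 h it is 65% and 41%. A negligible-tail argument may suit the gamma phase; it does not suit an observed slope slower than 24 h.

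**6. Can an earlier slope stand in?** With beta 40% and gamma 1–5% of AUC, a 3, 4, 24 h slope recovers 87–90% of the true AUC0-infinity, and a 24–48 h slope recovers 96–99%.

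**7. Effect of unequal windows.** I compared AUC0-infinity from samples to 48 h (4, 24, 48 h slope) with that from samples to 24 h (4, 24 h slope) for the same curve, with beta 20–60% and gamma 1–30%. The ratio is raised by about 4–7% at beta 16.8 h and about 5–16% at beta 24–30 h. With a 24–48 h slope in cycle 1 the shift can reach about a quarter.

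**The case against.** The strongest reply is that 'terminal' already has a meaning here. Section 3.1.4.2 calls 16.8 h a distribution half-life and 391 h the terminal one, so 10.2.1 may say only that the gamma half-life will not be characterised from one or two days of sampling. On that reading no patient is selected by his or her own pharmacokinetics, and an earlier slope would serve well enough for a 2-fold criterion.

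Much of this stands. A reader might infer that the slowest-eliminating patients, or all 6, will have no valid primary value. The documents do not support that: nothing sets AUC to missing, and step 6 shows that an approximate value is available. A reader might also take 51–78% as the chance of losing at least one patient. Those figures need the fitted half-life to be centred on 16.8 h, whereas the slopes fitted through all points from 4 h in step 3 are mostly shorter.

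Section 2.2 also names short half-life patients as those it hopes to identify, and the rule does not touch them. Section 11.2.2 calls the secondary analyses hypothesis generating, and 11.2.1 will weigh the totality of the data.

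What does not stand is that the text is therefore sufficient. The earlier-slope reading is not written anywhere, and step 3 shows that the choice of points more than doubles the half-life, from 7.3 to 16.9 h.

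**Conclusion.** The conflict is in the current text and does not depend on any modelling: the primary endpoint requires extrapolation, 10.2.1 declines to determine the slope when it is long, and nothing replaces it. On the gamma reading the slope is undefined for everyone; on the observed-slope reading it is withheld according to the outcome.

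The practical size is uncertain. The chance that at least one of 6 exceeds 24 h runs from under 1% to about 80%, depending on an assumed median of 9.7–17.1 h and CVs of 0.3–0.5 borrowed from t1/2 of two other drugs. The bias from unequal windows, under assumed phase shares and linear kinetics, is modest beside a 2-fold limit. This should be fixed before analysis, but it does not invalidate the study.

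**What to change.** Replace the sentence in 10.2.1 so that it states the following:

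- The apparent terminal slope is estimated for every evaluable patient by one pre-stated rule that names the samples used.
- For the primary ratio, the same window (to 24 h) is used in both periods.
- That slope is used for AUC0-infinity and CL, and the extrapolated percentage is reported for each period.
- The ratio of AUC from 0 to 24 h is given as a sensitivity analysis that needs no extrapolation.
- Apparent half-lives over 24 h are reported as 'apparent, not the gamma half-life' and are not omitted.

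The rule should also say what is done if the 24 h sample is missing, since 8 of 9 phase 0 samples (89%) still meets the 80% criterion.

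The cost is a few sentences, with no new samples or patients. The downsides are that some AUC0-infinity values will carry a large, openly reported extrapolated fraction resting on few late samples, and that the 48 h sample is not used in the primary ratio.

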10.2.2 Analysis Method

The ^{14}C content in plasma is measured by liquid scintillation counting. The carboplatin concentration is calculated based on the ^{14}C content in the plasma specimens. C_{max} , $t_{1/2}$, and AUC of plasma carboplatin will be calculated for the carboplatin microdose setting and reported.

10.3 Assessment of Platinum-DNA Adducts in PBMCs

DNA containing ^{14}C oxaliplatin-DNA adducts will be extracted from PBMCs (collected according to **section 10.1**) at Accelerated Medical Diagnostics as described previously [58, 82]. The DNA samples will be quantified by micro spectrophotometry, aliquoted and then delivered to Lawrence Livermore National Laboratory (LLNL) at [name] for AMS analysis. Oxaliplatin-DNA adduct frequency levels (1-100 adducts per 10^8 nucleotides) will be reported. Comparison of oxaliplatin-DNA adduct levels in PBMC's to response data will be as described in **section 11.2**.

11 STATISTICAL CONSIDERATIONS

11.1 Statistical Design

This is a prospective feasibility diagnostic study of a phase 0 microdose of ^{14}C oxaliplatin to ascertain whether there is sufficient promise to proceed for further study.

11.2 Analysis Plan

11.2.1 Primary Analyses

For the primary endpoint of feasibility is defined in **section 8.2.1**. We will correlate dose normalized $\text{AUC}_{0-\infty}$ parameters from phase 0 microdosing with parameters from the therapeutic dose of oxaliplatin for evaluable patients (the criteria for evaluation are listed in **section 8.1**). While assessment of PK feasibility is the primary endpoint of this study, we will use the totality of the data, including assessment of DNA adduct formation in PBMCs to determine the future development of this assay.

11.2.2 Secondary Analyses

Given the small number of patients included in this pilot study, all secondary analyses will be considered hypothesis generating for the design of future confirmatory study.

11.2.2.1 For secondary endpoint 8.2.2.1, we will correlate PK parameters from microdosing with parameters from therapeutic doses of oxaliplatin. All parameters will be normalized for dose. We will present descriptive summaries (scatterplots, tables, mean, SD,

correlation coefficient) of the relationship between the two sets of parameters.

11.2.2.2 For secondary endpoint 8.2.2.2, we will correlate PK parameters from phase 0 microdosing with parameters from FOLFOX-integrated microdosing of oxaliplatin. We will present descriptive summaries (scatterplots, tables, mean, SD, correlation coefficient) of the relationship between the two sets of parameters.

11.2.2.3 For secondary endpoint 8.2.2.3 and 8.2.2.4, we will characterize the repair of DNA adducts in PBMC, using descriptive statistics (graphical summaries, mean, SD, box plots). Response rate and duration of disease control (DDC) will be measured according to RECIST 1.1 (**Appendix C**). The DDC is equivalent to progression free survival if an intermittent oxaliplatin strategy is not employed. Progression free survival will be calculated from the date of enrollment to the date of first objective evidence of radiographic progression (soft tissue or bone lesion) or date of death due to any cause, whichever occurs first. If an intermittent oxaliplatin strategy is chosen, we will define DDC as the addition of the initial PFS and the PFS of the reintroduction, except in case of progression at the first evaluation after FOLFOX reintroduction. Radiological assessment by the treating Investigator will be the primary report in this analysis. We hypothesize that higher levels of DNA repair will be associated with non-response and shorter duration of disease control.

11.2.2.4 For secondary endpoint 8.2.2.5, we will assess toxicity to both micordoses of [¹⁴C]oxaliplatin. Toxicities potentially related to [¹⁴C]oxaliplatin will be assessed from initiation of the study to at least 14 days after the administration of the FOLFOX-integrated microdose or until full recover of toxicity (whichever is longer). Safety will be assessed through summaries of adverse events and laboratory evaluations. Descriptive statistics will be used rather than inferential statistics.

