3.1.3 Dosage

The dose of ^{14}C oxaliplatin to be administered as a microdose may need to be modified (see **section 6.3.2**) based on the ^{14}C signal in genomic DNA isolated from patients after receiving one of the dose levels identified in the dose titration table (**Table 1**). The dose levels being evaluated were identified using the following rationale: Based on our ongoing clinical microdosing trial with ^{14}C carboplatin, the radioactive dose of ^{14}C carboplatin is 10^7 dpm/kg of patient body weight with a total carboplatin of 1% of therapeutic carboplatin with AUC of 6. Our pre-clinical studies with oxaliplatin dosing of cell lines indicate that the requirement for ^{14}C oxaliplatin is about 10 times less than ^{14}C carboplatin. We will begin this study at dose level 1, which we have already

demonstrated to be adequate and safe in a single breast cancer patient. Therefore, the start dose (Dose Level 1) of [¹⁴C]oxaliplatin will be 2×10^6 dpm/kg of body weight with the total oxaliplatin at 1% of therapeutic dose (**Table 1**). Based on the ¹⁴C signal in genomic DNA of peripheral blood mononuclear cells (PBMC) in patients after dosing with this dose level 1, the dose will be titrated up or down, if needed, and administered to separate patients with the goal of achieving a ¹⁴C signal at 10-100 times the background. Instructions for preparing the microdose formulation are presented in **section 6.3.1**.

Table 1. Dose titration table

Dose levels	[¹⁴ C]oxaliplatin (dpm/kg of body weight)	Total oxaliplatin (% of therapeutic dose)
-1	1×10^6	1%
1	2×10^6	1%
2	2×10^6	3%
3	10×10^6	3%

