3.2.3 Oxaliplatin (Eloxatin®)

a. Description

1. Oxaliplatin is a third generation platinum analog. Oxaliplatin contains a bulky carrier ligand, 1,2-diaminocyclohexane (DACH), not present in either cisplatin or carboplatin.
2. Molecular Formula: $C_8H_{14}N_2O_4Pt$
3. Molecular Weight: 397.3 g/mol

b. Pharmacology

Mechanism of Action: Oxaliplatin is a non-cell cycle specific, alkylating antineoplastic agent that inhibits DNA synthesis through the formation of Crosslinks between the N7 positions of two adjacent guanines (GG), adjacent adenine-guanines (AG), and guanines separated by an intervening nucleotide (GNG). These crosslinks inhibit DNA replication and transcription.

c. Pharmacokinetics

1. Absorption: NA
2. Distribution: oxaliplatin has a protein binding of 70-95% with longer in vitro exposure leading to higher protein binding rates. In addition, it has been demonstrated approximately 37% of platinum is taken up by erythrocytes. Steady state volume of distribution is approximately 35L.
3. Metabolism: Oxaliplatin is rapidly metabolized in plasma primarily by biotransformation. No unchanged oxaliplatin is found 2 hours after administration. Oxaliplatin demonstrates no cytochrome P450 metabolism. 17 known metabolites of oxaliplatin have been identified, monochloro DACH platinum, dichloro DACH platinum, and mono and diaquo DACH platinum, are cytotoxic.
4. Elimination: Platinum is predominately excreted through the kidney with a clearance of 9-17 L/hour. Elimination kinetics are triphasic with alpha, beta, and gamma half-lives of approximately 25.8 minutes, 16.8 hours and 391 hours. A very small (2%) amount of platinum is excreted in the feces.

d. Adverse Effects:

1. Refer to package insert or manufacturer website for the most complete and up to date information on contraindications, warning and precautions, and adverse reactions.
 - Cardiovascular: Dyspnea, coughing, hypertension, edema, chest pain
 - Dermatology: injection site reaction
 - Gastrointestinal: Stomatitis, nausea, vomiting, taste alteration, anorexia, diarrhea, gastrointestinal reflux
 - Hematologic: leucopenia, agranulocytosis, anemia, epistaxis, pancytopenia, and thrombocytopenia, febrile neutopenia
 - Immunologic: allergic reactions, anaphylaxis
 - Hepatic/Metabolic/Laboratory/Renal: hypokalemia, dehydration
 - Neurologic: peripheral neuropathy

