6.3 Phase 0 [¹⁴C]Oxaliplatin Microdose

6.3.1 Preparation and Administration of [¹⁴C]Oxaliplatin Microdose

The starting dose (Dose Level 1, **Table 1**) of [¹⁴C]oxaliplatin microdose to be administered in this study is 2×10^6 dpm/kg of body weight, with the total dose of both unlabeled and ¹⁴C-labeled oxaliplatin solution being 1/100th of the planned therapeutic dosage (85 mg/m²). Calculations of the therapeutic dose and microdose of oxaliplatin will use the Du Bois and Du Bois formula for BSA:

$$\text{BSA (m}^2\text{)} = 0.20247 \times \text{Height(m)}0.725 \times \text{Weight(kg)}0.425$$

The dose of [¹⁴C]oxaliplatin is calculated in the following formula using Dose Level 1 (2 X 10⁶ dpm/kg, 1% therapeutic dose):

$$2 \times 10^6 \text{ dpm/kg} \div (2.22 \times 10^9 \text{ dpm/mCi}) \div 54 \text{ mCi/mmol} \times 397 \text{ mg/mmol} = 0.0066 \text{ mg/kg}$$

The patient specific dose of [¹⁴C]oxaliplatin will be added to an infusion bag containing D5W. Unlabeled oxaliplatin will be added to a separate infusion bag also containing D5W. Both treatment dose of unlabeled oxaliplatin and ¹⁴C-labeled oxaliplatin will be concurrently infused intravenously over 2 hours at the UC Davis Cancer Center Infusion Center. When these two infusion bags are concurrently administered to a patient, together they achieve a total final oxaliplatin microdose of 1% of the therapeutic dose. A chemotherapy nurse will administer the unlabeled oxaliplatin. A Nuclear Medicine Technologist (CNMT) will administer the ¹⁴C-labeled oxaliplatin via Y-site connection to the unlabeled oxaliplatin.

As an example, a patient with a height of 1.7 m and a body weight of 75 kg will have a BSA of 1.86 m². This patient would be planned to receive a therapeutic oxaliplatin dose of 158 mg (85 x 1.86). This patient's microdose would then be 1.58 mg of total oxaliplatin containing 1.08 mg of unlabeled oxaliplatin for injection and 0.50 mg [¹⁴C]oxaliplatin solution. The above dosing calculation should be modified as appropriate for the other dose levels in **Table 1**. [name], [name] or their designees are the only authorized prescribers for the microdosing formulation. If the designee signs the pharmacy order form in [name] or [name] absence, the designee must notify [name] or [name] as soon as possible before dosing the patient.

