6.3.2 Modification of the radioactive microdose during the study

We will vary the radioactive dose of [¹⁴C]oxaliplatin (dpm/kg) in the patient's microdose by combining the [¹⁴C]oxaliplatin with unlabeled oxaliplatin until the desired radioactive dose and chemical microdose (total dose at 1/100th of the therapeutic dose) are obtained. This effectively varies the radiochemical specific activity of the microdose infusion. The dose of [¹⁴C]oxaliplatin (dpm/kg) for this feasibility study will be determined by measuring the ¹⁴C associated with genomic DNA isolated from patient's PBMCs after microdosing. A ¹⁴C signal 10-100 times background is acceptable for this study. Of note, the sensitivity for pharmacokinetic analysis is much higher and we do not expect dose modification to have any impact on pharmacokinetic feasibility.

We will start [¹⁴C]oxaliplatin at 2 X 10⁶ dpm/kg of body weight, and add unlabeled oxaliplatin to 1% of the therapeutic oxaliplatin as calculated based on the dose of 85 mg/m². This dose level was demonstrated to be adequate and safe in a single breast cancer patient in a prior study. Two patients will be recruited to this dose level (Dose

Level 1). If the ^{14}C signal in PBMC genomic DNA is sufficient, dose level 1 will be used for the rest of the study. If the ^{14}C signal is insufficient or too high, the dose level will be titrated up or down, respectively, based on the ^{14}C signal as outlined in **Table 1**, and administered to two additional patients per dose level until a sufficient ^{14}C signal is obtained. If no ^{14}C signal can be detected in the genomic DNA at Level 3, no further escalation will be performed.

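### Two descriptive secondary PK analyses need repair: 11.2.2.1 normalises for dose parameters that do not scale with dose, and 11.2.2.2 does not measure the within-patient variation that objective 1.2.2 sets against 5%

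*Combined protocol and SAP*

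**What the plan says.** **Dose normalisation.** Endpoint 8.2.2.1 covers PK parameters other than the primary AUC, with Cmax, tmax, t1/2 and CL as examples, "of the phase 0 microdose compared to the therapeutic dose". The matching analysis, 11.2.2.1, plans a correlation plus scatterplots, tables, means, SDs and a correlation coefficient, and states without exception: "All parameters will be normalized for dose". Elsewhere the plan is narrower. The primary endpoint (8.2.1) compares AUC "when normalized for differences in dose", and 11.2.1 applies normalisation to AUC only. Section 10.2.2 says that Cmax, t1/2 and AUC "will be calculated for the carboplatin microdose setting and reported", with no mention of normalisation (it names carboplatin where the trial gives oxaliplatin).

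**Intrapatient variation.** Objective 1.2.2 is to validate that intrapatient variation of exposure to the microdose is below 5%. The matching endpoint (8.2.2.2) compares the phase 0 microdose with the FOLFOX-integrated microdose and names no metric. Section 11.2.2.2 plans a correlation and the same list of descriptive summaries. The 5% appears only in the objective. No section defines a within-patient CV, an interval for it, or a rule for judging it. Section 11.2.2 calls all secondary analyses hypothesis generating.

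**The concern.** Dose normalisation makes two doses comparable when a parameter rises in proportion to dose. Under linear kinetics AUC and Cmax do. A half-life and a time to peak do not, and clearance is dose divided by AUC, so dose has already been taken out. Dividing these by dose creates a difference where none exists. What is at stake is the table comparing microdose and therapeutic-dose kinetics, part of what the pilot hands to the next study.

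On 1.2.2, a correlation coefficient says how well patients keep their rank and spacing across two occasions. It depends on how far patients differ from each other as well as on how far each patient varies. Means and SDs of the two sets describe the group on each occasion. None of the listed outputs is a within-patient variation that can be held against 5%, so a named objective has no defined answer. Section 2 lists intrapatient variability among the key secondary objectives, and 2.5 sets a long-term goal of delivered AUC within 10% of target, so the figure matters for development.

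**Working it through.** **(a) Size of the artefact**

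Inputs: the worked example in 6.3.1 (therapeutic dose 85 × 1.86 = 158.1 mg; microdose 1% = 1.581 mg); Table 1 in 3.1.3 (levels 2 and 3 at 3%, so 4.743 mg); and, for illustration, the 16.8 h half-life in 3.2.3, which lists "half-lives of approximately 25.8 minutes, 16.8 hours and 391 hours".

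Suppose t1/2 is truly 16.8 h at both doses:

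| Divisor: total oxaliplatin | Result |
|---|---|
| Therapeutic, 158.1 mg | 16.8 / 158.1 = 0.106 h/mg |
| Microdose at 1%, 1.581 mg | 16.8 / 1.581 = 10.6 h/mg |
| Microdose at 3%, 4.743 mg | 16.8 / 4.743 = 3.54 h/mg |

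The artificial ratio is 100 at 1% and 33 at 3%. Dividing by mg/m² gives the same ratio: 16.8/85 = 0.198 against 16.8/0.85 = 19.8. The same factor applies to tmax and CL. The 33-fold figure arises only if the 3% levels of Table 1 are used; 6.3.2 describes the "total dose at 1/100th of the therapeutic dose", and those two places need reconciling.

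Two limits:
- Section 6.1 gives the same amount of [¹⁴C]oxaliplatin on both occasions. If the divisor is the ¹⁴C dose, it is equal on both sides and there is no gap.
- A factor that is the same for every patient cancels in r. The harm is then to tables, means and SDs. If each value is divided by that patient's own mg dose, the factor is not constant and r can move: for unrelated values with a CV of 30%, the shared divisor alone gives r of about 0.10–0.20, assuming a BSA CV of 10–15%.

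**(b) Why r does not answer 1.2.2**

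Inputs: AUC mean 4.68, SD 1.40 (2.2, therapeutic dose). CV = 1.40/4.68 = 29.9%, assumed here to hold for the microdose. A 15% spread is a second, purely assumed value. Lognormal AUCs with equal variance on both occasions are assumed.

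Formula: true r on the log scale = 1 − within-patient variance / total variance.
- Spread 29.9%: total log variance = ln(1 + 0.299²) = 0.0857; within-patient variance at CV 5% = 0.05² = 0.0025; r = 1 − 0.0025/0.0857 = 0.971.
- Spread 15%: total log variance = ln(1 + 0.15²) = 0.02225; r = 1 − 0.0025/0.02225 = 0.888.

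The same 5% gives two different correlations. Sampling error blurs this further. In a simulation of 300,000 sets of six pairs at the 29.9% spread, the central 95% of observed r runs from about 0.83 to 0.998 when the within-patient CV is 5%, and from about 0.42 to 0.99 when it is 10%. The ranges overlap almost entirely above 0.83.

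**What a within-patient CV from the same data would give**

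Within-patient CV = SD of the log ratio / √2. With six pairs it has 5 df, so the 95% limits are the estimate times √(5/12.83) = 0.624 and √(5/0.831) = 2.453.

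| Observed CV | 95% CI |
|---|---|
| 2% | 1.2–4.9% |
| 3% | 1.9–7.4% |
| 5% | 3.1–12.3% |

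This statistic can be held against 5%. It also shows how little six pairs can settle.

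**The case against.** On (a), the sentence may be loose drafting. The primary endpoint's wording about differences in dose, and the absence of normalisation in 10.2.2, suggest what was meant, and a half-life tabulated in h/mg would probably be noticed. A divisor based on ¹⁴C dose would remove the gap. This stands as a limit on the harm. It does not rescue the sentence, which is the only normalisation instruction for this comparison and makes no exception.

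On (b), the plan calls these analyses hypothesis generating and lists scatterplots and tables. With six patients the paired AUCs yield a within-patient CV directly, and an SD of differences could be worked back from the two SDs and r. Group means would show a common shift. All of that is right: what is missing is a named metric and its interval, not data. It does not remove the mismatch between an objective to validate a 5% limit and an analysis in which that limit never appears.

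A reader might infer that the trial is too small for 1.2.2. Under an assumed rule that a one-sided 95% upper limit must fall below 5%, six pairs would pass with probability 79%, 33% or 12% at true CVs of 2%, 3% or 4%. The plan states no such rule, so these figures are illustration only and do not show an error in the sample size, which 11.3 ties to a different quantity. A reader might also infer that the 100-fold artefact reaches the feasibility conclusion. It does not: 8.2.1 and 11.2.1 rest on dose-normalised AUC, where normalisation is correct.

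**Conclusion.** Both parts hold, confined to descriptive secondary analyses.

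(a) As written, the rule gives a wrong result for tmax, t1/2 and CL: 100-fold apart at 1% and 33-fold at 3%, conditional on total oxaliplatin being the divisor. An attentive analyst would probably catch it.

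(b) This is the more substantive part. Objective 1.2.2 has no defined answer, and r cannot supply one: 0.97 or 0.89 at the same 5% CV. Those values rest on carrying a therapeutic-dose spread over to the microdose and on the assumed 15%; the conclusion that r depends on between-patient spread does not.

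Both should be corrected before the PK data are analysed. Neither bears on the validity of the primary comparison.

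**What to change.** **11.2.2.1.** Replace the normalisation sentence with: *AUC and Cmax will be normalised for dose; t1/2, tmax and CL will be compared without normalisation.*

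**11.2.2.2.** Add: *From paired log ¹⁴C AUCs, each divided by the administered ¹⁴C dose and computed over the same sampling window for both microdoses (0–24 h, the last time common to Tables 2 and 3), we will report the geometric mean ratio with 95% CI and the within-patient CV (SD of the log ratio / √2) with a chi-square 95% CI (5 df for 6 patients).* The ¹⁴C basis is needed because conversion to total oxaliplatin would put the two occasions about 100-fold apart at the 1% level. The common window is needed because phase 0 sampling ends at 24 h and cycle 1 sampling at 48 h. The geometric mean ratio captures a common shift, which the CV removes.

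State as well that the second microdose is given with full-dose oxaliplatin and FOLFOX, so the ratio mixes repeatability with dose-level and co-treatment effects.

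**1.2.2.** Reword to: *To estimate the intrapatient variation of exposure to a [¹⁴C]oxaliplatin microdose, for comparison with a 5% target.*

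**Cost.** One sentence replaced, two or three added and one objective reworded; no new samples, patients or assays. The downside is that the claim of validation below 5% is given up. Keeping it would require a stated criterion and a sample size justified against it.
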